### **8.3    Follow-up of Adverse Events**

All adverse events will be followed with appropriate medical management until resolved. Patients removed from study for unacceptable adverse events will be followed until resolution or stabilization of the adverse event. For selected adverse events for which administration of the investigational drug was stopped, a re-challenge of the subject with the investigational drug may be conducted if considered both safe and ethical by the Investigator.

### **8.4    Adverse Events Monitoring**

All adverse events, whether or not unexpected, and whether or not considered to be associated with the use of the study drug, will be entered into OnCore®, as noted above.

The Investigator will assess all adverse events and determine reportability requirements to the UCSF Data and Safety Monitoring Committee (DSMC) and UCSF's Institutional Review Board, the Committee on Human Research (CHR); and, when the study is conducted under an Investigational New Drug Application (IND), to the Food and Drug Administration (FDA) if it meets the FDA reporting criteria..

All adverse events entered into OnCore® will be reviewed by the Helen Diller Family Comprehensive Cancer Center Site Committee on a weekly basis. The Site Committee will review and discuss at each weekly meeting the selected toxicity, the toxicity grade, and the attribution of relationship of the adverse event to the administration of the study drug(s).

All grade(s) 3-5 adverse events entered into OnCore® will be reviewed on a monthly basis at the Site Committee meetings. The Site Committee will review and discuss the selected toxicity, the toxicity grade, and the attribution of relationship of the adverse event to the administration of the study drug(s).

In addition, all suspected adverse reactions considered “serious” entered into OnCore®, will be reviewed and monitored by the Data and Safety Monitoring Committee on an ongoing basis and discussed at DSMC meetings, which take place every six weeks.

## 8.5 Expedited Reporting

### **Reporting to the Data and Safety Monitoring Committee**

If a death occurs during the treatment phase of the study or within 30 days after the last administration of the study drug(s) and it is determined to be related either to the study drug(s) or to a study procedure, the Investigator or his/her designee must notify the DSMC Chair (or qualified alternate) within 1 business day of knowledge of the event. The contact may be by phone or e-mail.

### **Reporting to UCSF Committee on Human Research (Institutional Review Board)**

The Principal Investigator must report events meeting the UCSF CHR definition of "Unanticipated Problem" (UP) within 10 business days of his/her awareness of the event.

### **Reporting to Novartis**

Reporting of SAEs: The principal investigator has the obligation to report all serious adverse events to the Novartis Pharmaceuticals Drug Safety and Epidemiology Department (DS&E).

To ensure patient safety, every SAE, regardless of suspected causality, occurring

- after the patient has provided informed consent and until at least 30 days after the patient has stopped study treatment/participation
- after protocol-specified procedures begin (e.g., placebo run-in, washout period, double-blind treatment, etc.) and 30 days after the patient has stopped study treatment
- after the start of any period in which the study protocol interferes with the standard medical treatment given to a patient (e.g., treatment withdrawal during washout period, change in treatment to a fixed dose of concomitant medication) and until 30 days after the patient has stopped study treatment

must be reported to Novartis within 24 hours of learning of its occurrence (fax: [REDACTED]). This includes serious, related, labeled (expected) and serious, related, unlabeled (unexpected) adverse experiences. All deaths during treatment or within 30 days following completion of active protocol therapy must be reported within 5 working days.

Any SAEs experienced after this 30 day period should only be reported to Novartis if the investigator suspects a causal relationship to the study drug. Recurrent episodes, complications, or progression of the initial SAE must be reported as follow-up to the original episode within 24 hours of the investigator receiving the follow-up information. A SAE occurring at a different time interval or otherwise considered completely unrelated to a previously reported one should be reported separately as a new event. The end date of the first event must be provided.

The original copy of the SAE Report and the fax confirmation sheet must be kept within the Trial Master File at the study site.

Follow-up information is sent to the same fax number as the original SAE Report Form was sent, using a new fax cover sheet, stating that this is a follow-up to the previously reported SAE, and giving the date of the original report. Each re-occurrence, complication, or progression of the original event should be reported as a follow-up to that event regardless of when it occurs. The follow-up information should describe whether the event has resolved or continues, if and

---

how it was treated, whether the blind was broken or not (if applicable), and whether the patient continued or withdrew from study participation.

If the SAE is not previously documented in the everolimus Investigator Brochure or Package Insert (new occurrence) and is thought to be related to the Novartis study drug, a DS&E associate may urgently require further information from the investigator for Health Authority reporting. Novartis may need to issue an Investigator Notification (IN), to inform all investigators involved in any study with the same drug that this SAE has been reported. Suspected Unexpected Serious Adverse Reactions (SUSARs) will be collected and reported to the competent authorities and relevant ethics committees in accordance with Directive 2001/20/EC or as per national regulatory requirements in participating countries.

For Comparator Drugs/Secondary Suspects (Concomitant Medications), all serious adverse experiences will be forwarded to the comparator drug company by the investigator.

**Reporting of Pregnancy:** Preclinical data regarding reproductive toxicity is described in the most recent Investigator Brochure. The potential reproductive risk for humans is unknown. Women of childbearing potential should be advised to use highly effective contraception methods while they are receiving everolimus and up to 8 weeks after treatment has been stopped.

To ensure patient safety, each pregnancy occurring while the patient is on study treatment must be reported to Novartis within 24 hours of learning of its occurrence. The pregnancy should be followed up to determine outcome, including spontaneous or voluntary termination, details of the birth, and the presence or absence of any birth defects, congenital abnormalities, or maternal and/or newborn complications. The newborn will be followed for at least 12 months.

Pregnancy should be recorded on a Clinical Trial Pregnancy Form and reported by the investigator to the oncology Novartis Drug Safety and Epidemiology Department (DS&E). Pregnancy follow-up should be recorded on the same form and should include an assessment of the possible relationship to the study treatment and any pregnancy outcome. Any SAE experienced during pregnancy must be reported on the SAE Report Form.

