*In vivo* studies investigating the anti-tumor activity of everolimus in experimental animal tumor models showed that everolimus monotherapy typically reduced tumor cell growth rates rather than produced regressions. These effects occurred within the dose range of 2.5 mg to 10 mg/kg, orally once a day.

In preclinical models, the administration of everolimus is associated with reduction of protein phosphorylation in target proteins downstream of mTOR, notably phosphorylated S6 (p-S6) and p-4EBP1, and occasionally with an increase in phosphorylated AKT, a protein upstream of mTOR signaling pathway.

All significant adverse events observed in toxicology studies with everolimus in mice, rats, monkeys and mini-pigs were consistent with its anticipated pharmacological action as an anti-proliferative and immunosuppressant and at least in part reversible after a 2 or 4-week recovery period with the exception of the changes in male reproductive organs, most notably testes.

Further details can be found in the everolimus Investigator's Brochure.

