- 11. Patients who have a history of another primary malignancy, with the exceptions of: non-melanoma skin cancer, and carcinoma in situ of the cervix, uterus, or breast, unless the patient has been disease free for  $\geq 3$  years;
- 12. Patients with a history of non-compliance to medical regimens or who are considered potentially unreliable or will not be able to complete the entire study;
- 13. Patients who are currently part of or have participated in any clinical investigation with an investigational therapeutic drug within 1 month prior to dosing;
- 14. Pregnant or nursing (lactating) women;
- 15. Women of child-bearing potential (WOCBP), defined as all women physiologically capable of becoming pregnant, who are not willing to use adequate methods of contraception during the study and for 8 weeks after the end of treatment.  
Women are considered post-menopausal and not of child-bearing potential if they have had 12 months of natural (spontaneous) amenorrhea with an appropriate clinical profile (e.g. age appropriate, history of vasomotor symptoms) or have had surgical bilateral oophorectomy (with or without hysterectomy) or tubal ligation at least six weeks prior to randomization. In the case of oophorectomy alone, only when the reproductive status of the woman has been confirmed by follow up hormone level assessment is she considered not of child-bearing potential.
- 16. Male patients whose sexual partner(s) are WOCBP who are not willing to use adequate contraception, during the study and for 8 weeks after the end of treatment

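### The pregnancy reporting rule in Section 8.5 stops when study treatment stops, while the protocol's own contraception period runs 8 weeks longer, and partner pregnancies are not explicitly addressed

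*Combined protocol and SAP*

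**What the plan says.** Section 8.5, under Reporting to Novartis, has a separate rule for pregnancy: "each pregnancy occurring while the patient is on study treatment must be reported to Novartis within 24 hours of learning of its occurrence". Follow-up hangs on that rule: "The pregnancy should be followed up to determine outcome", and "The newborn will be followed for at least 12 months". A closing paragraph names the form to use and who receives it, but gives no time limit.

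The paragraph just before the rule describes the reproductive risk in humans as unknown. It advises women to use contraception "while they are receiving everolimus and up to 8 weeks after treatment has been stopped". Section 5.1 uses the same length of time. Exclusion criterion 15 rules out women of child-bearing potential "who are not willing to use adequate methods of contraception during the study and for 8 weeks after the end of treatment". Criterion 16 sets the matching rule for men, with the 8 weeks again counted from when treatment ends: "Male patients whose sexual partner(s) are WOCBP who are not willing to use adequate contraception, during the study and for 8 weeks".

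SAE reporting in Section 8.5 runs "after the patient has provided informed consent and until at least 30 days after the patient has stopped study treatment/participation". After those 30 days an SAE goes to the company only if the investigator suspects the drug. Section 8.1.2.3 counts a congenital anomaly or birth defect as serious, but does not list pregnancy itself.

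Table 7-1 places the last serum pregnancy test at the visit 28 days (+/- 7) after therapy. If the patient cannot attend, a telephone toxicity check may replace that visit. Under Section 7.1.3, patients off therapy are then followed for PFS and OS only.

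**The concern.** The protocol asks patients to avoid pregnancy for 8 weeks after treatment because the human risk is not known. A pregnancy that begins in those weeks is the event the precaution is meant to prevent, and its outcome would be informative. The reporting rule, taken as written, does not ask for it, and the follow-up of the pregnancy and the child depends on that rule.

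Exclusion criterion 16 extends the precaution to men with partners who could become pregnant. No section says whether a partner's pregnancy is to be reported, or how information would be obtained from someone who is not a trial participant. A site that follows the text exactly could learn of such a pregnancy and have no clear duty to report or follow it.

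**Working it through.** The plan states no figure to reproduce, so the check compares time windows counted from the end of treatment.

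**Inputs**
- Contraception period: 8 weeks (Section 8.5; exclusion criteria 15 and 16).
- Pregnancy reporting after treatment: 0 days (Section 8.5).
- SAE reporting regardless of cause: at least 30 days (Section 8.5).
- Last scheduled pregnancy test: day 28 +/- 7 (Table 7-1).

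**Steps**
1. Contraception period in days: 8 x 7 = 56.
2. Part of it outside the pregnancy reporting rule: 56 - 0 = 56 days, the whole period.
3. Part of it in which even an SAE is reportable only on suspicion of causality, taking the 30-day minimum: 56 - 30 = 26 days.
4. Range of the last test: 28 - 7 = day 21 to 28 + 7 = day 35. Days left with no later test: 56 - 35 = 21 at best, 56 - 21 = 35 at worst. With a telephone check in place of the visit there may be no post-treatment test at all.

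Step 4 describes the schedule, not detection: a single test need not reveal every conception before it. The test also falls inside the 56 days, so the plan may produce a positive result from a conception after the last dose with no stated duty to report it.

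**Could another provision fill the gap?**

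| Provision | Reaches the 8 weeks after treatment? |
|---|---|
| 24-hour pregnancy rule, with outcome and newborn follow-up (8.5) | No |
| SAE reporting (8.5) | Serious events only; after day 30 only if the drug is suspected |
| Pregnancy form paragraph (8.5) | No window given; unclear |
| Unanticipated Problems to the IRB (8.5) | No cut-off stated, but not a rule for every pregnancy, and no outcome follow-up |
| Post-treatment visit (Table 7-1) | One test, replaceable by telephone; no reporting duty attached |
| Long-term follow-up (7.1.3) | PFS and OS only |

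Two kinds of event remain that no provision clearly covers: an uncomplicated pregnancy, and a loss not judged serious. A birth defect after a post-treatment conception would come to light well past day 30, so the SAE route would depend on the investigator suspecting the drug.

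**The case against.** Five points can be made on the other side.

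- **Other routes exist.** A reader might infer that every pregnancy in the 8 weeks goes unreported and unfollowed. The documents do not support that. Serious outcomes can be reported as SAEs, any SAE during a pregnancy must be reported, and the form paragraph has no end date. This stands, and it limits the point to pregnancies without a serious event.
- **Partners may already be included.** A reader might infer that a partner's pregnancy is uncovered throughout a male patient's treatment. In the rule, the patient's treatment sets the time window; it does not say whose pregnancy counts, so a partner's pregnancy during treatment can be read into it. This also stands. What remains is that partners are not named, no route to their data is given, and even the wide reading ends with treatment.
- **The animal findings prove less than they seem to.** Section 1.2.1.3 reports at least partial reversibility "with the exception of the changes in male reproductive organs, most notably testes". A reader might take this as lasting damage, or as evidence of risk to a partner's pregnancy. The text concerns recovery periods of 2 or 4 weeks in animals and says nothing about partners' pregnancies. The point does not rely on it.
- **A contraception period need not equal a reporting period.** That is true in principle, so this is not a strict contradiction. But the plan gives no reason for the shorter window, and it already wants reported pregnancies followed to the newborn's first year.
- **Some material cannot be seen.** The consent pages were removed and the pregnancy form is not among the documents. Either might mention partners, so the partner part is held with less confidence.

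**Conclusion.** The point holds in a limited form. The duty to report and follow a pregnancy ends with treatment, 56 days before the protocol's own contraception period does. Within those days, nothing clearly requires reporting or follow-up of an uncomplicated pregnancy or a loss not judged serious, and partner pregnancies are not explicitly addressed at any time.

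The size in patients cannot be given. The trial plans 105 adults aged 18 or over, but the documents do not say how many could become pregnant or have a partner who could, and the events may be few. The conclusion assumes that the time limit in the pregnancy rule means what it says and that the undated form paragraph does not override it. The issue is one of safety reporting; sample size, error rates and the PFS analysis do not change.

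**What to change.** Reconcile the reporting window in Section 8.5 with the contraception period the protocol already sets. The rule could say that each pregnancy the site learns of, in a patient or in a male patient's partner, from the first dose until 8 weeks after the last dose of study drug, is reported within 24 hours and followed as the section already describes. Outcome follow-up of a partner's pregnancy would need her consent. The form paragraph should refer to the same window.

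No new week-8 call is needed. A pregnancy question can be added to an existing contact after treatment, for example the first 4-month MRI follow-up or, for patients not seen regularly in clinic, the 6-monthly telephone call. Both fall after the 8 weeks have ended. Section 7.1.3 would need a short exception to its statement that patients off therapy are followed for PFS and OS only.

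The cost is wording in the protocol and consent form, one question at a contact that already takes place, and an occasional partner consent. The change alters no dose, treatment schedule or contraception period.

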## **9 Statistical methods and evaluation of results**

### **9.1 Statistical methods**

The following definitions will be used for statistical analysis:

- **Response:** Response is based on the best response. The best response is defined as the best objective status assessed by the RANO criteria.
- **Progression-free survival:** Number of days from the day the patient was enrolled to the day the patient experiences an event of disease progression or recurrence or to the date of death if disease progression or recurrence is not reached. All events of disease progression or recurrence will be included, regardless of whether the event occurred while the patient was still taking drug or had previously discontinued study drug. All events of death will be included for patients who had not experienced disease progression or recurrence. If the patient does not have an event of disease

---

progression or recurrence nor has the patient died, the patient's data will be censored at the date of last contact with the patient.

- **Overall survival:** Number of days from the day the patient was enrolled until the date of death. If the patient is lost to follow-up, the patient's data will be censored at the date of last contact with the patient.

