#### **4 Study design**

Treatment for patients with previously untreated LGG will be selected by whether or not their tumor has ATRX loss and/or 1p/19q chromosomal co-deletion. If the tumor is ATRX lost or 1p/19q intact, then patients will be further selected by whether or not their tumor demonstrates activation of the PI3K/mTOR pathway. If activation is present, patients will be treated in Arm 1 with single-agent everolimus at 10 mg daily continuously. If activation is not present, patients will be treated in Arm 2 with combined everolimus and TMZ. Everolimus will be given at 10 mg daily continuously, and TMZ will be dosed initially at 150 mg/m^2/day for 5 days out of a 28-day cycle. If ATRX is intact, 1p/19q co-deletion should be confirmed, or if only 1p/19q co-deletion is available and present, patients will be treated in Arm 3 with single-agent everolimus at 10 mg daily continuously. In all arms, treatment with everolimus will continue for up to 24 cycles, after which patients will be followed with interval MRIs until progression. In Arm 2, TMZ will be stopped after 12 cycles.

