### 7.1.3 Follow-up Assessments

- Protocol Completion Assessment:

- After administration of everolimus for two years, patients will have completed study treatment.
- All patients must be observed for safety for 30 days following the last dose of everolimus prior to withdrawal from study. This defines completion of active study participation.
- Physical examination and comprehensive neurologic examination and grading, vital signs including weight, Karnofsky Performance status, all laboratory values, and MRI of the brain must be repeated within 4 weeks of the last day of study only if these have not been evaluated within 14 days, inclusive, prior to the date of withdrawal from study, if patients are able to return to do so. If patients are unable to return for an in-person visit, then they will be contacted by phone to assess toxicity at approximately 4 weeks after that last day of study.
- Quality of Life Surveys (optional): 2 surveys will be completed 1 year post-completion of treatment or at the time of tumor progression if sooner than 1 year post-completion of treatment.
- Long-term Follow-up:
  - After completion of study treatment, patients whose tumors have not progressed will be followed with interval MRIs. These should be done every 4 months (+/- 2 weeks) for 1 year, then every 6 months (+/- 4 weeks) for an additional 2 years, and thereafter as per the discretion of the managing physician.
  - Patients will be followed according to routine clinical practice after removal from protocol therapy or until death, whichever occurs first.
  - Patients removed from protocol therapy for unacceptable adverse events will be followed until resolution or stabilization of the adverse event.
  - Patients off protocol therapy will continue to be followed for PFS and OS only for the purposes of this protocol. If patients are not being seen regularly in clinic, then phone calls for PFS and OS will be made every 6 months.

**Table 7-1** Visit evaluation schedule (note: 1 cycle = 28 days)

Procedures:	Initial Screen	1-month Assessment (by phone)	Assessments every 2 cycles (+/- 7 days unless otherwise noted) for cycles 1-12 of therapy	Assessments every 3 cycles (+/- 7 days unless otherwise noted) for cycles 13-24 of therapy	28 days after completing protocol therapy (+/- 7 days) †	Long Term Follow-Up
Clinical Evaluation: ‡						
Medical History	X					
Vital Signs and KPS ¥	X		X	X	X	
Physical Exam, Neurologic Exam	X		X	X	X	

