Toxicity Check	X £	X	X	X	X	
Pulse Oximetry	X		X	X	X	
ECG	X					
QoL questionnaires	X		X §			
Laboratory/ Diagnostic Tests: ‡						
Serum pregnancy for women of child-bearing potential	X	Day 28 (+/- 7 days) while on therapy			X	
CBC with diff and platelets*	X	Arms 1 and 3: Day 28 (+/- 7 days) while on therapy Arm 2: Day 21 (+/- 3 days) and day 28 (+/- 3 days) from 1 st day of temozolomide treatment while on dual therapy with both drugs, then Day 28 (+/- 7 days) while on everolimus alone			X	

Chemistries & liver function tests*	X	Day 28 (+/- 7 days) while on therapy	X	
Fasting cholesterol / triglycerides*	X	Day 28 (+/- 7 days) while on therapy	X	
MRI of the brain**	X	X	X	X ±
Hepatitis B/C testing*	X			
Tissue testing for treatment selection***	X			
Translational Research:				
Archival tumor tissue	X			
Research blood draw****	X			
Survival				X ±

\*See sections 7.1.1 and 7.1.2 for lists of specific tests to be ordered at screening and during treatment, respectively

\*\*With optional MRS at baseline, end of cycles 2 and 6, and at the time of tumor progression

\*\*\* See section 7.3.2 for specific tests to be done

\*\*\*\*If sample not already available in UCSF Tissue Bank

†If patients are unable to return for an in-person visit, a phone toxicity check will be acceptable

‡Vital signs include temp, BP, heart rate, respiratory rate, and weight. Height will be done at screening only.

§At screening, “toxicity check” refers to assessment of baseline conditions

¶Please refer to protocol text (Section 7.1) for time windows for all assessments. Phone contact for survival is also acceptable as per protocol text.

§Surveys will be filled out at the end of every 6 cycles while on treatment and then at 1 year post-completion of treatment or at the time of tumor progression if sooner than 1 year post-completion of treatment

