## 7.2.2 Imaging Time Points

Standard anatomic MR imaging will be performed as outlined in Table 7. The full imaging examination described above will optionally be performed at baseline, at the end of cycles 2 and 6, and at the time of suspected progression. The anatomic imaging components are standard of care, with the other parts being research add-ons. After the end of treatment and prior to progression, patients will be followed with anatomic imaging alone. The goal will be to determine whether the parameters estimated from advanced imaging are early predictors of response to therapy.

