- (1) development of new lesions or increase of enhancement (radiological evidence of malignant transformation);
- (2) a 25% increase of the T2 or FLAIR non-enhancing lesion on stable or increasing doses of corticosteroids compared with baseline scan or best response after initiation of therapy, not attributable to radiation effect or to comorbid events;
- (3) definite clinical deterioration not attributable to other causes apart from the tumour, or decrease in corticosteroid dose; or
- (4) failure to return for evaluation because of death or deteriorating condition, unless caused by documented non-related disorders

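### PFS is censored at last contact, so a patient who is no longer scanned but still reachable counts as progression-free at month 33 (38)

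*Combined protocol and SAP*

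**What the plan says.** Section 9.1 counts PFS from enrolment to progression, recurrence or death. For a patient with none of these it closes with "nor has the patient died, the patient's data will be censored at the date of last contact with the patient". OS has the same censoring date. No disease assessment is required to support event-free PFS time.

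On follow-up, Section 7.1.3 says: "If patients are not being seen regularly in clinic, then phone calls for PFS and OS will be made every 6 months". For patients taken off therapy it says: "Patients will be followed according to routine clinical practice after removal from protocol therapy or until death, whichever occurs first". The footnote to Table 7-1 says: "Phone contact for survival is also acceptable as per protocol text".

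Progression under 7.2.3 is partly clinical, but its radiographic criteria (new lesions, more enhancement, or "a 25% increase of the T2 or FLAIR non-enhancing lesion") need a scan.

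The plan also contains safeguards:

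- Section 4 describes 24 cycles of everolimus, "after which patients will be followed with interval MRIs until progression".
- Section 7.2.2 adds: "After the end of treatment and prior to progression, patients will be followed with anatomic imaging alone". This is not limited to patients who complete treatment.
- Section 7.1.3 gives completers an MRI every 4 months for a year, then every 6 months for two years.
- Clinical deterioration counts as progression (7.2.3), and Section 9.1 says: "All events of death will be included for patients who had not experienced disease progression or recurrence".
- Section 9.5 times the primary analysis to when landmark status is known for everyone. Section 9.5.2, however, also lets it start once all patients have completed 33 (38) months on study.

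**The concern.** Take a patient whose last MRI is at month 15 and who answers a phone call at month 34. Under 9.1 this patient stays in the Kaplan-Meier risk set, event-free, through month 33. A phone call cannot exclude growth on T2 or FLAIR imaging. Unless progression comes to light some other way, a silent progression between months 15 and 33 is recorded as success.

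Patients removed from therapy early are the most exposed, because the dated MRI calendar in 7.1.3 is written for those who have completed treatment. No sentence says that a phone contact is insufficient for PFS. Each arm is read against a fixed 50% (Section 9.3), so there is no control arm in which the same error would cancel.

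**Working it through.** **Inputs from the plan.** Threshold 50%, alternative 70%, 35 patients per arm, one-sided 90% limit, stated 86% (9.3); 95% CI (9.5.2); landmarks 33 and 38 months; 53-month accrual (9.5.1); treatment of 24 x 28 = 672 days, and 672/30.44 = 22.1 months.

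**Assumptions not in the plan.** A share f stops MRI before the landmark and stays reachable past it. A share d of their later progressions comes to light with the right date. PFS is exponential, and stopping is unrelated to prognosis.

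**1. The plan's own figure.** The smallest count r with P(X >= r | 35, 0.5) <= 0.10 is 22, with probability 0.0877. Then P(X >= 22 | 35, 0.7) = 0.865. The stated 86% reproduces as power.

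**2. Bias in closed form.** Let the landmark be L and the hazard ln2/L, so that true PFS at L is 50%. A patient who stops MRI at time u progresses between u and L with probability exp(-hazard x u) - 0.5.

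- Stop time uniform on 0 to L: average = 0.5/ln2 - 0.5 = 0.721 - 0.5 = 0.221. Bias = f x (1 - d) x 0.221, the same for 33 and 38 months.
  - f = 10%: +2.2 points (d = 0), +1.1 (d = 0.5).
  - f = 20%: +4.4 and +2.2.
- Stop time uniform on the 22.1-month treatment period, L = 33: hazard x 22.1 = 0.464, and (1 - exp(-0.464))/0.464 - 0.5 = 0.800 - 0.5 = 0.300.
  - f = 10%: +3.0 and +1.5.
  - f = 20%: +6.0 and +3.0.

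One patient of 35 is 2.9 points, so these shifts run from under half a patient to about two.

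**3. Simulation of the current rule.** 40,000 trials per setting, n = 35, true PFS-33 50%, stop time uniform on 0 to 33 months, Greenwood log-log limits:

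| Stop MRI | Later progressions found | Mean PFS-33 | 90% limit above 50% | 95% CI above 50% |
|---|---|---|---|---|
| 0 | - | 50.1% | 8.9% | 2.1% |
| 10% | none | 52.2% | 13.7% | 3.7% |
| 10% | half | 51.1% | 11.2% | 2.9% |
| 20% | none | 54.5% | 20.3% | 6.5% |
| 20% | half | 52.2% | 14.0% | 3.9% |

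With all found, the mean is 50.0% at both shares.

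**4. When contact also lapses.** If contact ends within 12 months of the last MRI, the means at 10%/20% stopping are 50.6/51.3% (none found), 49.7/49.6% (half) and 49.0/47.9% (all). The direction can reverse.

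**5. Censoring at the last MRI, later-found progressions kept as events.** Means at 10%/20% stopping:

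- Analysed exactly at the landmark: 50.1/50.0% (none found), 49.3/48.4% (half), 48.5/47.0% (all).
- Follow-up spread over the 53-month accrual: 49.6/49.1% (half), 49.1/48.2% (all).
- Stoppers progressing at 1.5 times the hazard of others: 50.6/51.3% (none) and 49.8/49.5% (half), against 52.6/55.2% and 51.4/52.6% under last contact.

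False success at half detection is 7.8/6.2% on the 90% limit.

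**The case against.** The harm needs a chain: MRI stops, contact continues, progression is silent, and calls made for the purpose of PFS miss it. The plan schedules frequent scans, calls anatomic MRI standard of care, intends imaging until progression, and counts deterioration and death as events. All of this is true and keeps the likely size down. None of it says what a phone contact can establish.

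The simulation assumes progression is seen continuously while scans go on. In fact completers' scans fall near months 26.1, 30.1, 34.1 and 40.1. If progression is dated at the detecting scan (the plan does not say), a true 50% reads as 0.5^(30.1/33) = 53.1% at month 33 and 0.5^(34.1/38) = 53.7% at month 38, with no dropout and under either censoring rule. This stands, and it means the absolute figures above depend on the model. The contrast survives: on that calendar, at half detection, last contact gives 54.0/54.9% at 10%/20% stopping, against 52.3/52.1% for last-MRI censoring (4,000 trials per setting).

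The replacement rule has a bias of its own, because progressions found after the last MRI count while negative phone contacts do not. With full detection the current rule is closer to the truth. This also stands, and is why last contact should remain as a sensitivity analysis.

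Two smaller points are fair. Section 9.5.2 computes a 95% CI without stating a test against 50%, so the last column of the table is one possible reading. The Table 7-1 footnote names only survival but defers to the text, so it does not by itself contradict 7.1.3.

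**Conclusion.** The concern holds. As written, the rule credits unscanned but reachable patients with progression-free time through the landmark, and the safeguards reduce this without closing the gap. For those patients the error is upward, by about 1 to 6 points across the settings in steps 2 and 3. No detection is the upper bound, since deaths and clinical deterioration are events.

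The size rests on assumed shares of 10-20% stopping MRI and on how many later progressions surface; the plan gives neither. It should be fixed because the change is cheap and the remaining error is mostly conservative against the fixed threshold. Confidence is moderate, because the frequency is unknown and the sign depends on contact patterns.

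**What to change.** - **Section 9.1, PFS.** Replace the censoring sentence with wording such as: *Patients without progression or death are censored at the last adequate disease assessment showing no progression (an MRI assessable by RANO, including scans done elsewhere; enrolment date if there is none after baseline).* Keep last contact for OS. Keep all deaths and all documented progressions as primary events, including those after missed scans.
- **Section 7.1.3.** State which assessment calendar applies to patients removed early, so that missed scans can be defined (for example, two consecutive planned MRIs). At each phone contact, request the date and report of any outside MRI, whether or not it shows progression.
- **Sensitivity analyses.** (a) Last-contact censoring, as now. (b) Events first reported after missed scans censored at the last adequate assessment. At half detection the new primary analysis and (a) bracket the true 50% (49.3-51.1% at 10% stopping, 48.4-52.2% at 20%), and (b) gives 50.0% if stopping is unrelated to progression.
- **Reporting.** Per arm, the number censored before the landmark and the gap from last MRI to last contact.

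**Cost.** Wording, two extra analyses, and collection of outside scan dates and reports. Power at true PFS 70% on the one-sided 90% limit falls from 0.87 without dropout to 0.85/0.83 at 10%/20% stopping (none found) or 0.83/0.79 (half found). On the 95% CI it falls from 0.65 to 0.57/0.54 or 0.55/0.49. The current rule at half detection shows about 0.70/0.72 on the 95% CI in smaller runs, but part of that is the upward bias itself.
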